# 5.2 Product Structural Composition

- Powered stapler consists of stapler body, arm rod, reload-resisting base, reload base, battery pack or power adapter.
- The cartridge component is composed of reload, reload-pushing piece and anastomotic nail, etc.

#### **5.3 Product Performance**

The main technical indicators of electric stapler include convenient replacement of stapler components, reliable positioning. In addition, the stapler is equipped with a safety protection device for empty staple

Version No.: 1.1/Version date: 20190325 Clinical Trial on Performance and Safety of Disposable Powered Articulating Endoscopic Linear Cutter Stapler in Total-Thoracoscopic Anatomic Lobectomy (segmentectomy)

cartridge to maintain its reliability. The product shall be sterile.

## 5.4 Trial Scope

The product is intended for thoracoscopic anatomical lobectomy (segmentectomy).

# 6. Product Applicable Scope, Contraindications and Precautions

#### 6.1 Applicable Scope

The Disposable Powered Articulating Endoscopic Linear Cutter Stapler is intended for transection, resection, and/or creation of anastomoses. The instrument has application in multiple open or minimally invasive general, gynecologic, urologic, thoracic, and pediatric surgical procedures. It can be used with staple line or tissue buttressing materials. The instrument may also be used for transection and resection of liver parenchyma (hepatic vasculature and biliary structures), pancreas, kidney and spleen.

## 6.2 Contraindications

- Do not use the instruments on the aorta.
- Do not use the instruments on ischemic or necrotic tissue.
- Do not use any linear cutter on major vessels without making provision for proximal and distal control.
- Tissue thickness should be carefully evaluated before firing any stapler. Refer to Reload Product Codes for tissue compression requirement (closed staple height) for each staple size. If tissue cannot comfortably compress to the closed stale height, or easily compresses to less than the closed staple height, the tissue is contraindicated as it may be too thick or too thin for the selected staple size.
- These instruments are not intended for use when surgical stapling is contraindicated.

#### 6.3 Cautions

See the IFU for details.

#### 6.4 Precautions

See the IFU for details.

# 6.5 Application Method

See the IFU for details.

# 7. Reference Medical Device-Related Information

#### 7.1 Stapler Information

Product name	ECHELON Flex Powered Articulating Endoscopic Linear Cutters
Specification/model	PSE45A, PCE45A, PLE45A, PSE60A, PCE60A, PLE60A
Registration No.	GXZJ 20173226240

	The product is a sterile device for single patient use, consisting of closing rod, red firing
	lock, firing handle, anvil release button, lithium battery pack, battery pack-releasing
Structural	piece, hole cover plate for manual override maintenance, knife-reversing switch, knob,
composition	articulation fins, reload alignment slot, anvil jaw and reload jaw. The lithium battery
	pack must be installed prior to use. The product has been sterilized by irradiation. This
	product is provided for single use.
Applicable scope	The Disposable Powered Articulating Endoscopic Linear Cutter Stapler is intended for
	transection, resection, and/or creation of anastomoses. The instrument has application in
	multiple open or minimally invasive general, gynecologic, urologic, thoracic, and
	pediatric surgical procedures. It can be used with staple line or tissue buttressing
	materials. The instrument may also be used for transection and resection of liver
	parenchyma (hepatic vasculature and biliary structures), pancreas, kidney and spleen.
Manufacturer	Ethicon Endo-Surgery, LLC
Agent	Johnson & Johnson Medical (Shanghai) Ltd.

## 7.2 Reload Information

Product name 1	echelon 60 ENDOPATH STAPLER Endoscopic Linear Cutter Reloads
Specification/model 1	ECR60W
Registration No. 1	GXZJ 20153080094
Structural composition 1	The linear cutter stapler reload is composed of cartridge, anastomotic nail and reload-protecting board, in which the material of anastomotic nail is Ti3Al2.5V. The reload is sterilized by radiation and provided for single use.
Product name 2	ECHELON 45 ENDOPATH Stapler Endoscopic Linear Cutter and Reloads
Specification/model 2	ECR45M, EC45, SC45, ECLG45, ECR45W, ECR45B, ECR45D, ECR4 5G
Registration No. 2	GXZJ 20163654883
Structural	The product is composed of anvil, trigger, firing trigger, handle and cartridge
composition 2	component. The reload is sterilized by radiation and provided for single use.
Product name 3	ECHELON FLEX Articulating Linear Cutters and Reloads Articulating Endoscopic Linear Cutter Reloads
Specification/model 3	EC45A, SC45A, EC45AL, EC60A, SC60A, LONG60A, ECR60W, ECR 60B, ECR60D, ECR60G, ECR60T, ECR60M
Registration No. 3	GXZJ 20173656323

Structural composition 3	This product is composed of stapler and cartridge. Its components include cartridge,
	closing rod, firing rod, rotary knob, articulating piece, manual knife-reversing switch,
	trip count indicator, knife direction indicator, anvil release button, closing rod, and
	anvil. The stapler is made of stainless steel, and the anastomotic needle is made of
	titanium alloy (Tianium3A12.5V). The product is sterilized by radiation.
Applicable scope	It is used for transection, resection and/or anastomosis. It can be used in a variety of
	open or minimally invasive general, gynecologic, urologic, thoracic, and pediatric
	surgical procedures. It can be used with staple line or tissue buttressing materials.
	These devices can also be used for transection and resection of liver parenchyma
	tissues (hepatic vasculature and biliary structures), pancreas, kidney and spleen.
Manufacturer	Ethicon Endo-Surgery, LLC
Agent	Johnson & Johnson Medical (Shanghai) Ltd.

# 8. Overall Design

#### 8.1 Test Design

#### 8.1.1 Primary objective

To evaluate whether the primary effectiveness evaluation indicator "device cutting and anastomosis success rate" of the Disposable Powered Articulating Endoscopic Linear Cutter Stapler manufactured by Fengh Company is non-inferior to the similar product manufactured by Johnson & Johnson Company in total-thoracoscopic anatomic lobectomy (segmentectomy).

#### 8.1.2 Secondary objectives

To evaluate whether there are differences in the secondary evaluation indicators (operation time, anastomosis time, incidence of chest tube drainage for more than 7 days, rate of conversion to thoracotomy, number of staple line repair needles) when the Disposable Powered Articulating Endoscopic Linear Cutter Stapler manufactured by Fengh Company is used in VAT anatomical lobectomy (segmentectomy) compared with the similar product manufactured by Johnson & Johnson Company.

To evaluate whether there are differences in the safety evaluation indicators (incidence of staple line dehiscence, incidence of staple line bleeding, incidence of air leakage, incidence of staple line infection, incidence of SAE (serious adverse event), incidence of AE (adverse event), incidence of device defects) between the Disposable Powered Articulating Endoscopic Linear Cutter Stapler manufactured by Fengh Company and the similar product manufactured by Johnson & Johnson Company in total-thoracoscopic anatomic lobectomy (segmentectomy).

To evaluate whether there are differences in the operational performance evaluation indicators (operational performance evaluation of the stapler) between the Disposable Powered Articulating Endoscopic Linear Cutter Stapler manufactured by Fengh Company and the similar product manufactured by Johnson & Johnson Company in total-thoracoscopic anatomic lobectomy (segmentectomy).

#### 8.1.3 Selection of test method and reasons

This clinical trial is a "prospective, multi-center, stratified-block randomization, incomplete blinding, parallel positive control, non-inferiority test".

- (1) Prospective: A research method that tracks from the present to the future. Prospective studies can clarify the causal relationship; uniform diagnostic, detection, and evaluation criteria can be available for the obtained data, the data processing therefore is controllable.
- (2) Multi-center: 5 clinical trial institutions were selected to conduct this clinical trial. The application of multi-center trial can allow to obtain more cases than those of single-center trial in the same time, the clinical trial time therefore can be shortened; since the multi-center trial is completed by different regions, different trial centers and many clinical researchers, the conclusion therefore is often widely representative.
- (3) Stratified block randomization: This trial adopts the stratified block randomization method (with the study site as the stratification factor) and the randomization envelope to randomize the subjects who are screened successfully. The randomized-grouping time is that before the surgery. Randomized grouping ensures that, except for treatment factors, other non-treatment factors that may have confounding effect are kept consistent in each group as far as possible, so as to ensure the balance of baseline of each group; randomized-grouping allows each subject to have equal opportunity to be assigned to the test group or control group.
- (4) Incomplete blinding: Since the investigational medical device and the control medical device are different in appearance, while the subjects are under anesthesia during the operation, the grouping arrangement can not be known. Therefore, the method of incomplete blinding is used, that is, the investigators knows the grouping result, while the subject does not know the grouping result. Blinded data review is also required at the same time. Incomplete blinding can minimize the bias caused by "placebo effect", and make the evaluation of adverse reactions by subjects more objective.
- (5) Parallel positive control: The investigational medical device has the mature application technology with many similar products that are marketed at home and abroad. It has been used in clinical practice for many years, with exact effect and predictable occurrence of adverse events. Therefore, parallel positive control is adopted in this clinical trial.

(6) Non-inferiority test: To evaluate whether the main effectiveness evaluation indicator "success rate of cutting and anastomosis" of the Disposable Powered Articulating Endoscopic Linear Cutter Stapler manufactured by Fengh Company is non-inferior to the similar product manufactured by Johnson & Johnson Company in total-thoracoscopic anatomic lobectomy (segmentectomy). The purpose of the non-inferiority test is to validate that if the effectiveness and safety of the investigational medical device is lower than those of the control device. The difference should be less than the pre-defined non-inferiority margin, that is, the difference should be acceptable in clinical practice.

#### 8.1.4 Measures for reducing and avoiding bias

- (1) Before the start of the study, the sponsor shall provide relevant training for the investigators participating in the study to ensure that the investigators fully understand the study process and are familiar with the operation of the study device; during the study, the investigators shall operate in strict accordance with the operating methods and procedures in the study protocol, and the clinical trial monitor shall do a good job in quality control and monitoring to ensure that the investigators operate and implement in strict accordance with the study protocol. The above measures shall be implemented throughout the implementation phase of the study to reduce errors or operational errors.
- (2) Subjects shall be screened in strict accordance with the clinical diagnostic criteria, as well as the inclusion and exclusion criteria of the trial protocol to reduce selection bias.
- (3) VAT anatomical lobectomy (segmentectomy) is difficult to operate. Thoracoscopic anatomical lobectomy (segmentectomy) requires high operating skills and should be carried out in centers with rich experience in thoracoscopic surgery. In view of the learning curve of thoracoscopic anatomical lobectomy (segmentectomy), doctors can be more proficient based on at least 50 cases. The operating surgeon who is recommended to perform thoracoscopic lobectomy (segmentectomy) should be experienced in at least 100 cases of thoracoscopic anatomic lobectomy (segmentectomy).
- (4) When the clinical trial is completed, the data storage and collation shall be done well. When data problems are found, the data analyst shall check and confirm the data through the data clarification form to avoid recording errors.

# 8.1.5 Investigational medical device and control medical device or control diagnosis and treatment method

See the corresponding IFU for the diagnosis and treatment method with the investigational medical device and the reference medical device. The investigators shall truthfully record the usage for reference.

When subjects experience adverse events related to the stapler, the investigators should truthfully judge the correlation between adverse events and the test device.

#### 8.1.5.1 Contraindications of video-assisted thoracoscopic surgery

- (1) Active stage of tuberculosis.
- (2) The pulmonary pleura is extensively adherent and the pleural space is atretic.
- (3) The general condition is poor and the infection is not effectively controlled.
- (4) Patients with poor pulmonary function who can not tolerate intraoperative one-lung ventilation anesthesia and pneumonectomy.

#### 8.1.5.2 Preparation

The requirements for anesthesia are the same as or even higher than those for common thoracotomy; and thoracotomy is required if thoracoscopic treatment can not be adopted. Preoperative diagnostic tests should be conducted to further understand the condition of the lesion, know the presence or absence of concomitant diseases and general condition, so as to help determine whether to adopt the thoracoscopic surgery, surgical method and surgical date to make a better decision.

#### 8.1.5.3 Medical history and physical examination

Thorough and accurate disease history collection is the first step in preoperative preparation. In addition to inquiring about the history of major diseases, the past history of the subject should also be detailed. In particular, it is necessary to understand whether there is a history of thoracic tuberculosis, pleurisy, chest trauma, surgery and hydropneumothorax. Since these diseases will alter the normal anatomy of the pleural space, the thoracoscopic surgery therefore is difficult or impossible. In addition, attention should be paid to the health of the patient's cardiovascular and respiratory systems to understand whether intraoperative one-lung ventilation and surgical trauma can be tolerated. Systematic preparation is another important part of preoperative preparation, which is helpful for the diagnosis and detection of concomitant diseases and shall be focused on.

#### 8.1.5.4 Laboratory examination

Preoperative routine blood, urine and stool examination shall be conducted to find abnormalities. Reexamination shall be timely carried out and the causes shall be found. If low hemoglobin indicates anemia and malnutrition; a small number of blood transfusions can be given to make hemoglobin close to normal levels in a short period of time, which improves the safety of surgery. Abnormalities in water electrolyte tests should be corrected before surgery. Liver and kidney function tests can help understand the functional status of liver and kidney organs and surgical tolerance. Since intrathoracic hemorrhage itself is not easy to stop spontaneously, the subject's coagulation function should be examined before surgery. If the subject has a history of coronary heart disease in the near future before surgery, myocardial enzyme examination should be performed. Routine blood glucose tests can detect some asymptomatic patients with type II diabetes.

#### 8.1.5.5 Auxiliary examination

Chest X-ray examination is a quick and effective method to understand the intrathoracic condition. Chest X-ray, chest radiography, tomography and CT can be performed according to the needs of the disease. CT examination should generally be done to provide more information about the disease and intrathoracic structure for researchers and provide a more sufficient basis for preoperative surgical planning. Preoperative ECG examination is helpful to understand the heart condition, and echocardiography and myocardial imaging can also be done when necessary. Ultrasonography can examine pleural effusion and abdominal organs. Preoperative pulmonary function test is very important. In addition to the determination of total pulmonary function, it is also necessary to determine the split pulmonary function when conditions permit, so as to have an objective estimate of the subject's surgical tolerance.

#### 8.1.5.6 Mental preparation

The necessity and possible discomfort of the surgery should be patiently introduced to the subjects to relief the subjects' ideological concerns and enhance the confidence of surgical treatment, which can help subjects to better cooperate with the thoracoscopic surgery.

## 8.1.5.7 Preoperative routine preparation

The preparation one day before thoracoscopic surgery and on the day of surgery is the same as the preparation before thoracotomy for similar diseases. If the thoracoscopic Operation time is expected to be short, a catheter may not be indwelled. The blood matching volume is also relatively less, and a small amount of blood or no blood matching can be performed according to specific circumstances. Since the thoracoscopic surgery needs to be timely converted into thoracotomy in case of lesions or complications that can not be treated with thoracoscopy during thoracoscopic surgery, thoracotomy instruments should also be prepared for emergency use.

# 8.1.5.8 Preoperative respiratory function estimation

Although thoracoscopic surgery has little effect on the pulmonary function of subjects, the pulmonary complications after thoracoscopic surgery mainly stem from the low pulmonary function of subjects. The subjects' preoperative pulmonary function should be known.

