#### 8.1.6.3 Exclusion criteria

#### Subjects meeting any of the following conditions can not be included:

- (1) Subjects are with video-assisted thoracoscopic surgery-related contraindications;
- Subjects' preoperative imaging findings indicate severe pleural adhesions and significantly calcified hilar lymph nodes;
- (3) Subjects with platelet (PLT)  $< 60 \times 10^{9}$ /L or international normalized ratio (INR) > 1.5;
- (4) Subjects with forced expiratory volume in one second (FEV1)/predicted value  $\leq$  50%, or forced expiratory volume in one second (FEV1)/forced vital capacity (FVC)  $\leq$  60%;
- (5) Subjects with ejection fraction  $\leq 50\%$ ;
- (6) Subjects with major organ failure or other serious diseases (including clinically relevant cardiovascular disease or myocardial infarction within 12 months prior to enrollment; severe neurological or psychiatric history; preoperative severe infection that must be controlled by medication; active disseminated intravascular coagulation; high risk of thrombosis);
- (7) Subjects who are pregnant or lactating women;
- (8) Subjects participating in other drug or device clinical trials within 1 month before the trial;
- (9) Other situations not suitable for inclusion judged by the investigators.

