#### (3) Incidence of chest tube drainage greater than 7 days

**Justification for selection:** Staple line healing is an important indicator for effectiveness and safety evaluation of such products. Therefore, the healing rate of staple line is selected as one of the indicators to evaluate the product performance. However, since the healing of staple line is not easy to be observed, and postoperative chest tube drainage is a routine operation of VAT lobectomy (segmentectomy), the removal of chest tube drainage indicates that the staple line has gradually healed. Meanwhile, the *Guidelines for Technical Review of Endoscopic Stapler Registration* issued by NMPA (original CFDA) on March 13, 2017 is referred to. Eventually, the "incidence of chest tube drainage greater than 7 days" is used as an alternative indicator for evaluation.

**Evaluation time:** After surgery.

**Mode of evaluation:** The investigators not involving in the subject's treatment judge that whether the subject could remove the chest drainage tube, and record the time when the subject finally removes the chest drainage tube. The time is accurate to day (natural day).

**Calculation formula:** Incidence of chest tube drainage for more than 7 days = number of subjects in each group with chest tube drainage for more than 7 days/total number of subjects in this group  $\times$  100%.

**Precautions:** ① In order to avoid the evaluation bias caused by subjective reasons, whether the subjects can remove the chest drainage tube should be independently judged by the investigators who do not participate in the treatment of subjects; ② For the subjects with chest tube drainage for more than 7 days, the possible reasons for chest tube drainage for more than 7 days should be analyzed to determine whether it is related to the device.

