#### (6) Incidence of AE (adverse event)

Evaluation time: During the whole clinical trial process.

Formula: Incidence of adverse events = number of subjects with adverse events in this group/number of all subjects in this group  $\times$  100%.

**Definition:** An adverse event is any untoward medical occurrence in a clinical investigation, whether or not related to the device. It is necessary to analyze the postoperative vital signs and laboratory tests (blood routine, biochemical indicators, etc.).

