### 8.2.5.2 Laboratory examinations 

- Blood routine: hemoglobin (Hgb), red blood cell count (RBC), white blood cell count (WBC), neutrophil count (NEUT), neutrophil ratio (NEUT%), platelet count (PLT);
- (2) Coagulation blood routine: prothrombin time (PT), activated partial thromboplastin time (APTT), international normalized ratio (INR);
- (3) Cardiac examination: ECG, cardiac ejection fraction;
- (4) Blood biochemistry: aspartate aminotransferase (AST), alanine aminotransferase (ALT), serum total bilirubin (STB), serum albumin (ALB), serum creatinine (Scr), blood urea nitrogen (BUN);
- (5) Pulmonary function test: forced expiratory volume in one second (FEV1)/predicted value, forced expiratory volume in one second (FEV1)/forced vital capacity (FVC);
- (6) Arterial blood gas analysis: pH, oxygen partial pressure, carbon dioxide partial pressure, oxygen saturation (SpO2);
- (7) Blood pregnancy test: applicable to women of childbearing age  $(18 \sim 50 \text{ years old})$ ;

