### 9.5 Qualification/Disqualification Criteria for Clinical Trial Results

The non-inferiority hypothesis is tenable if the lower limit of 95% confidence interval of the difference in the primary effectiveness evaluation indicator "device cutting and anastomosis success rate" between the test group and the control group is greater than the non-inferiority critical value (-10%).

The secondary effectiveness evaluation indicators and safety evaluation indicators are tested by difference test, and the significance level is set at 0.05. If the test result of the difference in any secondary evaluation indicator and safety evaluation indicator between the test group and the control group is p > 0.05, then there is no significant difference in this indicator between the test group and the control group.

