# 9.7 Statistical Methods of Data, Together with Processing Methods of Missing, Unused or Wrong Data and Unreasonable Data

#### 9.7.1 Statistical method for data

Statistical analysis is performed using the SAS 9.1 software.

Statistical description on all data, including demographic data, baseline data, all efficacy indicators and all safety data shall be performed. Measurement data will be statistically described using mean, standard deviation, minimum, maximum, median, 25th percentile and 75th percentile; enumeration data will be statistically described using frequency and percentage.

The primary effectiveness evaluation indicator (device cutting and anastomosis success rate) is evaluated by the confidence interval method.

The secondary evaluation indicators are evaluated by the difference test. Measurement data are compared using two independent samples t-test. Enumeration data are compared using Pearson's  $X^2$  test or Fisher's

exact test.

The safety evaluation indicators are evaluated by the difference test. Measurement data are compared using two independent samples t-test. Enumeration data are compared using Pearson's  $X^2$  test or Fisher's exact test. The adverse events and device defects occur in this trial shall be shown in list.

The stapler operational performance is evaluated by the difference test, with the Pearson's  $X^2$  test or Fisher's exact test.

The central effect is considered in the analysis process. The general linear model is used for measurement data, and CMH is used for enumeration data.

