- (11)Respiratory insufficiency: Incision pain, chest wall activity limitation, cough and weakness, airway secretion retention after pneumonectomy may cause atelectasis and inflammation, coupled with flatulence and other factors will cause respiratory insufficiency, manifested as shortness of breath, difficulty, rapid pulse, restlessness, elderly patients and even confusion. Blood gas tests show a decrease in PO2 and PCO2 in the early stage, followed by an increase in PCO2. Chest X-ray shows partial or total atelectasis of the remaining lungs. Once this disease is suspected, secretions in the airway should be immediately removed in addition to oxygen inhalation. If fiberoptic bronchoscopy suction does not work, tracheotomy should be considered and mechanical breathing should be performed if necessary. This complication often occurs in people with poor lung function. Therefore, pulmonary function assessment is very important. Antibiotics, bronchodilators, smoking cessation, chest physiotherapy, postural drainage and appropriate exercise can improve pulmonary function and reduce the occurrence of postoperative respiratory insufficiency.
- (12)Massive atelectasis: The incidence of massive and severe atelectasis after lobectomy has been reported to be about 7.8%, and the incidence after right upper or right upper middle lung resection is higher than that after right lower or left lobectomy (15.5%, 6%). Patients present with shortness of breath, varying degrees of cyanosis, shortness of breath, accelerated heart rate, and even high fever. Careful physical examination and chest X-ray can help in the diagnosis. Once the diagnosis is confirmed, tracheal and bronchial aspiration and lavage should be performed immediately.
- (13)Lobar torsion and gangrene: Lobar rotation of 180° or more along the bronchovascular pedicle, called

lobar torsion, is mostly caused by excessive intraoperative traction and inversion of the lobe. In addition, if the oblique and horizontal fissures are fully developed, the right middle lobe is prone to torsion after resection of the right upper lobe or right lower lobe. After lung lobe torsion, it causes vascular occlusion, which in turn causes pulmonary infarction and pulmonary gangrene. Once this disease is suspected, the chest should be opened immediately. If the twisted lobe remains viable, it can be reduced and fixed in its normal position. Otherwise, lobectomy should be performed.

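### Chest drainage beyond 7 days is compared without screening FEV1 % predicted, a baseline value the plan requires and treats as prognostic; the test is valid but forgoes a modest, nearly free gain in precision

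*Combined protocol and SAP*

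**What the plan says.** Section 8.1.5.8, on preoperative respiratory function, says that "the pulmonary complications after thoracoscopic surgery mainly stem from the low pulmonary function of subjects" and that this function should be known before surgery. Section 14.1.5 (11) says of respiratory insufficiency: "This complication often occurs in people with poor lung function. Therefore, pulmonary function assessment is very important".

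The measurement is among the required tests in section 8.2.5.2 ("Pulmonary function test: forced expiratory volume in one second (FEV1)/predicted value") and is scheduled at Visit 1 in section 8.2.7.1. Exclusion criterion (4) in section 8.1.6.3 ("Subjects with forced expiratory volume in one second (FEV1)/predicted value" at or below 50%, or FEV1/FVC at or below 60%) cannot be applied without it.

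Drainage beyond 7 days is a per-subject yes/no secondary indicator (section 8.1.7.2 (3)): "number of subjects in each group with chest tube drainage for more than 7 days/total number of subjects in this group". For such indicators section 9.7.1 says "Enumeration data are compared using Pearson's" chi-square or Fisher's exact test, and allows for centre through CMH. Section 9.5 adds: "The secondary effectiveness evaluation indicators and safety evaluation indicators are tested by difference test, and the significance level is set at 0.05", and takes p above 0.05 to mean no significant difference. Randomization is stratified by site only (section 8.1.3). No baseline covariate appears anywhere in section 9.

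**The concern.** The plan names a prognostic factor, requires its measurement before surgery, and then uses it in neither the stratification nor the analysis of the indicator to which it is most plausibly relevant. With a binary outcome, adjusting for a prognostic baseline variable usually raises the power to detect a real difference between arms. Under section 9.5 a non-significant result reads favourably for the test stapler, so even a small avoidable loss of power works in that direction.

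Timing also matters. Section 9.8 treats any analysis not pre-specified as exploratory, so an adjusted result added after lung function turned out unbalanced would carry little weight. Section 9.1 leaves the SAP open until database lock, so it can be specified there.

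**Working it through.** **1. The plan's own sample size.** Inputs from section 9.2.1: success rate 97% in both arms, margin 10 points, one-sided α 0.025, power 80%.

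n₃ = 2 × 0.97 × 0.03 × (1.960 + 0.842)² / 0.10² = 45.68.

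n₄ = 45.68 × [1 + √(1 + 4/(0.1 × 45.68))]² / 4 = 64.1, so 65 per arm.

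65 / (1 − 0.20) = 81.25, so 82 per arm and 164 in total. This reproduces the plan's figure. No power is stated for any secondary or safety indicator.

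**2. Unadjusted power for drainage beyond 7 days.** The documents give no rate for this endpoint. The nearest figure is 15.2% for prolonged air leak after pneumonectomy (section 14.1.5 (16)), used here as an assumed proxy. For 15.2% against 30.4%, two-sided 0.05 and 82 per arm, the pooled rate is 0.228:

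- Null SE = √(2 × 0.228 × 0.772 / 82) = 0.0655.
- Alternative SE = √((0.152 × 0.848 + 0.304 × 0.696) / 82) = 0.0644.
- Power = Φ[(0.152 − 1.96 × 0.0655) / 0.0644] = Φ(0.366) = 64%.

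For 15.2% against 25% the same formula gives 35%.

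**3. Effect of adding FEV1.** The association is assumed: odds ratio per SD of 1, 1.5, 2 or 3 (log-odds slope 0, 0.41, 0.69 or 1.10). Simulation with 10,000 trials per row, 82 per arm, a standard normal covariate and marginal rates held fixed; simulation error is about 0.5 point. LR is the likelihood-ratio test from a logistic model.

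| Rates | OR per SD | Pearson | LR, arm only | LR, arm + FEV1 | Gain over Pearson |
|---|---|---|---|---|---|
| 15.2% v 30.4% | 1 | 64.8 | 65.4 | 65.3 | 0.5 |
| | 1.5 | 65.6 | 66.2 | 67.0 | 1.4 |
| | 2 | 65.3 | 66.0 | 68.8 | 3.5 |
| | 3 | 64.1 | 64.8 | 71.8 | 7.7 |
| 30% v 50% | 1 | 74.8 | 75.2 | 75.5 | 0.7 |
| | 1.5 | 75.0 | 75.3 | 77.3 | 2.3 |
| | 2 | 74.5 | 74.7 | 79.3 | 4.8 |
| | 3 | 74.9 | 75.1 | 84.1 | 9.2 |

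Of each gain, 0.2 to 0.7 point comes from the LR test itself. With equal rates of 15.2% or 30%, the adjusted test rejected in 4.8% to 5.7% of trials.

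A separate simulation with an arm log-odds of 1.0 gave gains of about 0 to 1 point at slopes 0 to 0.25, 2 to 3 at 0.5, and 3 to 7 at 0.8. Cutting off the low tail of FEV1, as exclusion (4) does, changed little.

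**4. Sparse events.** Section 9.2.3 allows a centre as few as 16 subjects. At an 8% event rate (0.08 × 164 ≈ 13 events) with equal centres of about 33, one centre has no event with probability 0.92³³ = 0.064. At least one of five does with probability 1 − (1 − 0.064)⁵ = 28%, and that centre's coefficient cannot then be estimated. With sparse events and five centres in the model, the test also becomes mildly anti-conservative. A threshold of 20 events corresponds to 20/164 = 12.2%.

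**The case against.** Several counter-arguments stand.

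- Section 8.1.5.8 concerns pulmonary complications only and gives no strength of association. Section 8.1.5.15 closes by calling this material reference guidance for investigators. Section 14.1.5 (11) speaks of one complication, respiratory insufficiency, and does not call lung function the main driver of complications in general.
- Section 8.1.7.2 (3) justifies the drainage indicator as a stand-in for staple-line healing. That FEV1 predicts it is a reasonable inference, not a statement in the plan.
- Exclusion (4) removes the subjects with the worst lung function.

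A reader might infer that the same adjustment belongs on overall AE and SAE incidence. The documents do not support that. In section 8.1.8 (6), "An adverse event is any untoward medical occurrence in a clinical investigation, whether or not related to the device"; SAEs are likewise not confined to pulmonary events, and section 8.1.8 (5) counts staple-line adverse events among them.

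A reader might also infer that leaving FEV1 out biases the comparison. It does not. An imbalance of 1.96 × √(2/82) = 0.31 SD or more arises by chance in 5% of trials of this size and, at slopes of 0.5 to 1.1, would shift the raw difference by about 2 to 6 points. The error rate of the unadjusted test already allows for such imbalance.

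Finally, the low power of the secondary and safety comparisons arises because 164 subjects were sized on the primary endpoint alone. A doubling from 15.2% still has only 67% to 72% power after adjustment at odds ratios of 1.5 to 3, and the section 9.5 reading of p above 0.05 is untouched.

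What survives is the narrow case: one indicator, a covariate already required, and a small gain.

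**Conclusion.** The point holds as a modest efficiency improvement of low severity. For drainage beyond 7 days, adjusting for FEV1 % predicted would add about 0 to 7 points of power at 82 per arm for slopes of 0 to 0.8 per SD. If FEV1 is not prognostic, there is little or no loss.

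This rests on three assumptions: that FEV1 predicts prolonged drainage, which the plan implies but does not state; that the slope lies in that range; and that the event rate is about 15% or more, where type I error stayed near 5%. Below about 12% the fallback would apply and nothing would change.

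It would go too far to say that the plan discards the power to detect a less safe stapler. The planned test is valid, the loss is small, and the documents support no such statement for all-cause AE or SAE incidence.

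**What to change.** In section 9.7.1 and the SAP, before database lock, pre-specify for chest drainage beyond 7 days:

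- A logistic model with arm, centre and screening FEV1 % predicted (continuous), reported as a standardised risk difference with 95% CI and p-value.
- The Pearson/Fisher result shown alongside. This also keeps in view any subject without an FEV1 value, since section 9.7.2 (2) does not allow baseline values to be estimated.
- An exact fallback: drop the centre terms if any centre has no events; use Fisher's exact test alone if there are fewer than 20 events in total.

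Apply the same model to pulmonary AEs as a supportive analysis only. Leave overall AE and SAE incidence on the planned tests.

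The cost is a few lines of SAP text and one model per indicator, with no new data, visits or subjects. The small downside is a model-based estimate and a fallback rule to follow.
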